3.3.2 Study doses and control groups

3.3.2.1 Dosage selection

Pharmacokinetic analyses of the data collected with the immediate-release formulation of exenatide from 12 adolescent patients enrolled in Study 2993-124 concluded that adolescents have a faster rate of exenatide elimination than adults (clearance=14.7 L/hr and 9.57 L/hr, respectively; AstraZeneca, data on file). Despite this decrease in exposure, the results of this trial were consistent with clinical trials of exenatide conducted in adults, in that the administration of 5 µg exenatide was efficacious and well tolerated (Study 2993-124) ([Malloy et al, 2009](#)). BYETTA 10 µg BID is currently under investigation in adolescents with type 2 diabetes (Study H8O-MC-GWBQ).

Given the information from Study 2993-124, coupled with the results of previous studies with EQW conducted in adults, the 2 mg weekly dose of EQW will be examined in the current study. This dose regimen resulted in steady state exenatide concentrations that were well tolerated, and produced robust improvements in mean HbA1c and body weight in adults.

3.3.2.2 Control group

This is a double-blind, placebo-controlled study.

4 PATIENT SELECTION CRITERIA

Investigators should keep a record, the patient screening log, of patients who entered pre-study screening.

4.1 Population to be studied

A total of 77 male or female children and adolescents of 10 to <18 years of age, diagnosed with type 2 diabetes mellitus and treated with diet and exercise alone or in combination with a stable dose of oral antidiabetic agent (eg, metformin and/or SU) and/or insulin for at least 2 months prior to screening, will be randomized into this study to yield 70 evaluable patients.

At least 60% of study patients must be included for analysis of the primary and secondary endpoints (Evaluable Population) at Week 24.

At least 40% and not more than 60% of randomized study patients must be female.

At least 40% of patients should be recruited from areas with similar ethnicity and lifestyle to those of the European Union member states.

Each patient should meet all of the inclusion criteria and none of the exclusion criteria for this study. Under no circumstances can there be exceptions to this rule.

4.2 Inclusion criteria

For inclusion in the study patients should fulfil the following criteria:

1. Is a child or an adolescent of 10 to <18 years old, at Visit 1 (Screening)
2. Has been diagnosed with type 2 diabetes mellitus per American Diabetes Association diagnostic criteria
3. HbA1c of 6.5% to 11.0%, inclusive, in patients not taking insulin/SU, and of 6.5% to 12.0%, inclusive, in patients taking insulin/SU, at Visit 1 (Screening)
4. Has a C-peptide of >0.6 ng/mL at Visit 1 (Screening)
5. Has been treated with diet and exercise alone or in combination with a stable dose of an oral antidiabetic agent (eg, metformin and/or SU) and/or insulin for their type 2 diabetes for at least 2 months prior to Visit 1 (Screening)
6. Has a fasting plasma glucose concentration <280 mg/dL (15.5 mmol/L) at Visit 1 (Screening)
7. Either is not treated with or has been on a stable treatment regimen with any of the following medications for a minimum of 1 month prior to Visit 1 (Screening):
 - (a) Oral contraceptives (female patients)
 - (b) Antihypertensive agents
 - (c) Lipid-lowering agents
 - (d) Thyroid replacement therapy
 - (e) Antidepressant agents
8. Is male, or is female and meets all the following criteria:
 - (a) Not breastfeeding
 - (b) Negative serum pregnancy test result (human chorionic gonadotropin, beta subunit [β hCG]) at Visit 1 (Screening)
 - (c) If of childbearing potential, must practice and be willing to continue to practice appropriate birth control (defined as at least 1 method which results in a low failure rate, ie, less than 1% per year, when used consistently and correctly, such as implants, injectables, hormonal contraceptives, some intrauterine contraceptive

- devices, sexual abstinence, tubal ligation or occlusion, or a vasectomized partner) during the entire duration of the study and must not be planning to conceive
9. Has clinical laboratory test values (clinical chemistry, hematology, and urinalysis) judged as not clinically significant by the Investigator at Visit 1 (Screening)
 10. Has physical examination and ECG results deemed not clinically significant by the Investigator at Visit 2 (Week 0)
 11. Both patient and parent/caretaker are able to read, understand, and sign the Informed Consent Form (ICF) and Child Assent Form and if applicable, an Authorization to Use and Disclose Protected Health Information form, if applicable (consistent with Health Insurance Portability and Accountability Act of 1996 [HIPAA] legislation), communicate with the Investigator, and understand and comply with protocol requirements
 12. Both patient and parent/caretaker are able to read and understand the lifestyle modification program and the parent/caretaker is willing to assist the patient's adherence to the lifestyle modification program.

4.3 Exclusion criteria

Patients should not enter the study if any of the following exclusion criteria are fulfilled:

1. Has a clinically significant medical condition that could potentially affect study participation and/or personal well-being, as judged by the Investigator, including but not limited to the following conditions:
 - (a) Hepatic disease (defined by aspartate or alanine transaminase >3.0 times the upper limit of normal (ULN))
 - (b) Renal disease or serum creatinine >1.5 mg/dL (132.6 µmol/L) (males) or 1.4 mg/dL (123.8 µmol/L) (females)
 - (c) Gastrointestinal disease deemed significant by the Investigator
 - (d) Organ transplantation
 - (e) Chronic infection (eg, tuberculosis, human immunodeficiency virus, hepatitis B virus, or hepatitis C virus)
 - (f) Clinically significant malignant disease (with the exception of basal and squamous cell carcinoma of the skin) within 5 years of Visit 1 (Screening).
2. Has positive antibody titers to glutamic acid decarboxylase (GAD65) or islet cell antigen (ICA512) at Visit 1 (Screening)

3. Has a personal or family history of elevated calcitonin, calcitonin >100 ng/L, medullary thyroid carcinoma, or multiple endocrine neoplasia-2
4. Has donated blood within 2 months of Visit 1 (Screening), is planning to donate blood during the study, or has a hematocrit of <30%
5. Has had a major surgery or a blood transfusion within 2 months of Visit 1 (Screening)
6. Has received any investigational drug within 1 month (or 5 half-lives of the investigational drug, whichever is greater) of Visit 1 (Screening)
7. Has ever used exenatide (exenatide once weekly [exenatide LAR], exenatide BID, BYETTA, or any other formulation) or any glucagon-like peptide-1 (GLP-1) receptor agonist (eg, liraglutide [Victoza[®]])
8. Currently abuses drugs or alcohol or has a history of abuse that in the Investigator's opinion would cause the individual to be noncompliant with study procedures
9. Has known allergies or hypersensitivity to any component of study treatment (including PLG and Microsphere Diluent)
10. Has been treated, is currently being treated, or is expected to require or undergo treatment with any of the following medications:
 - (a) Oral glucocorticoids or corticosteroids within the last 30 days or more than 20 days within the past year. However, glucocorticoid treatment for some infections for less than 10 days is allowed
 - (b) TZD within 90 days prior to Visit 1 (Screening)
 - (c) Inhaled glucocorticoids at a dose equal to or above 1,000 µg Flovent[®] (fluticasone propionate) daily
 - (d) Weight loss medication(s) (including over the counter) within 30 days of Visit 1 (Screening)
 - (e) Alpha-glucosidase inhibitors, meglitinide, nateglinide, or pramlintide for >1 week in the 1 month prior to Visit 1 (Screening)
 - (f) DPP-4 inhibitors within 30 days prior to Visit 1 (Screening).
11. Has admitted use of anabolic steroids within the past 60 days or is planning use during the study

12. Is an immediate family member (spouse, parent, child, or sibling; biological or legally adopted) of personnel directly affiliated with the study at the clinical study site, or is directly affiliated with the study at the clinical study site
13. Is pregnant
14. Is employed by AstraZeneca (ie, an employee, temporary contract worker, or designee responsible for the conduct of the study).

5 STUDY CONDUCT

5.1 Restrictions during the study

Once screened and qualified for entry, patients will be instructed as follows:

- Take no new prescription medications or over-the-counter preparations without prior approval of the Investigator (who may contact the Sponsor for consultation). For restrictions on concomitant medications, refer to Section 5.6.
- Avoid strenuous exercise and alcohol 24 hours prior to each scheduled visit.
- Do not donate blood for the duration of the study.

The Sponsor should be contacted if the Investigator is informed of any restriction violations. The Sponsor will decide whether a patient with restriction violations will be allowed to continue study participation.

For procedures for withdrawal of incorrectly enrolled patients see Section 5.3.

5.2 Patient enrollment and randomization

The Principal Investigator will:

1. Obtain signed and dated informed consent from parent or caretaker and patient assent and HIPAA Authorization if applicable before any study specific procedures are performed.
2. Determine patient eligibility. See Sections 4.2 and 4.3.
3. The Interactive Voice Response System/Interactive Web Response System (IVRS/IWRS) will assign an eligible patient unique randomization code, beginning with '#'.

If a patient withdraws from participation in the study, then his/her enrollment/randomization code cannot be reused.

5.2.1 Procedures for randomization

Patients who meet all study requirements based on inclusion and exclusion criteria will be randomized and assigned to 1 of 2 treatment groups in 5:2 ratio (Group A:Group B) at Visit 2 (Week 0). The randomization will be stratified by baseline HbA1c (<9.0% or ≥9.0%) and country.

Study medication kits will be labeled with unique package numbers (this is **not** the patient randomization number). At Visit 2 (Week 0), the study-site pharmacist or other medically qualified personnel must contact the IVRS or the IWRS to randomly assign patients and for kit assignment. If medication is allocated to a patient incorrectly, the Sponsor must be notified.

The study-site personnel must call the IVRS/IWRS at all subsequent visits to record the visit and confirm the kit assignment. The calls to the IVRS/IWRS will ensure the resupply of additional kits required for upcoming visits.

5.3 Procedures for handling patients incorrectly enrolled or randomized

Patients who fail to meet the inclusion/exclusion criteria should not, under any circumstances, be randomized to receive study medication. There can be no exceptions to this rule. Patients who are screened, but subsequently found not to meet all the eligibility criteria must not be randomized or initiated on treatment. These patients (who have not been randomized) should be withdrawn from the study. Where a patient does not meet all eligibility criteria, but is randomized in error or incorrectly started on treatment, the Investigator should inform the study physician immediately, and a discussion should occur between the study physician and the Investigator regarding whether to continue or discontinue the patient from treatment. The study physician and the Investigator must ensure all decisions are appropriately documented.

5.4 Blinding and procedures for unblinding the study

5.4.1 Methods for ensuring blinding

The Sponsor, the study-site personnel, and the patients will be blinded to treatment allocation during the double-blind controlled assessment period. Every effort should be made to ensure that patients remain blinded to their treatment during this period.

The exception to the above is for those personnel analyzing the PK and antibody samples. The randomization information will be provided to ensure that only samples from patients who were on active study treatment are analyzed. Samples from patients not dosed with the relevant active study treatment will only be analyzed on a “for cause” basis, for example, if there is suspicion that a patient has been dosed incorrectly.

During the open-label extension period, the Sponsor, study-site personnel, and the patients will be unblinded to the identity of the study medication.

5.4.2 Methods for unblinding the study

Individual treatment codes, indicating the treatment randomization for each randomized patient, will be available from the IVRS/IWRS. Routines for this will be described in the IVRS/IWRS user manual that will be provided to each center.

The treatment code should not be broken except in medical emergencies when the appropriate management of the patient requires knowledge of the treatment randomization. The Investigator documents and reports the action to AstraZeneca, without revealing the treatment given to patient to the AstraZeneca staff.

AstraZeneca and the safety data entry site retain the right to break the code for serious adverse events (SAEs) that are unexpected and are suspected to be causally related to an investigational product and that potentially require expedited reporting to regulatory authorities. Treatment codes will not be broken for the planned analyses of data until all decisions on the evaluability of the data from each individual patient have been made and documented.

5.4.2.1 24-Week Controlled Assessment Period

The patient, Investigator (and all study-site personnel), and Sponsor will be blinded to treatment during the controlled assessment period. Every effort should be made to ensure that patients remain blinded to their treatment during this period. If a patient's treatment is unblinded only to a Global Safety Case delegate and related personnel required for case processing for the purpose of FDA submission, the patient's status in the study may remain unchanged. Otherwise, the code may be unblinded only after an irrevocable decision has been made to withdraw the patient from the investigational product and immediate knowledge of the study medication is needed to optimize the clinical management of the patient. The Investigator is to notify the AstraZeneca medical monitor if an event occurs that requires a patient's treatment assignment to be unblinded.

5.4.2.2 28-Week Extension Period

The patient, Investigator (and all study-site personnel), and Sponsor will be unblinded to study medication during the 28-week extension period.

5.5 Treatments

5.5.1 Identity of investigational product(s)

5.5.1.1 Prefilled syringes

Table 2 Identity of investigational product delivered via prefilled syringes

Investigational product	Dosage form and strength	Manufacturer
Exenatide once weekly (EQW)	2.0 mg powder for injection	AstraZeneca ^a
Placebo to match exenatide once weekly	Placebo powder for injection	AstraZeneca ^a

^a Responsible for supply of Investigational Product and placebo.

All study medication sufficient for 4-week treatment will be packed into patient kits. The vials containing the exenatide/placebo powder for injections will be packed into a small box containing 4 vials. Four prefilled syringes with diluent for suspension of EQW and matching placebo will be packed into another box also containing 6 vial adaptors and 6 23-Gauge×5/16 inch needles.

Study materials will be provided to patients by the Investigator or medically qualified subinvestigator named on Form FDA 1572, or other qualified study-site personnel. Under no circumstance will the Investigator or subinvestigators allow the study medication to be used other than as directed by the protocol or to be administered to any persons other than patients participating in the study. Medically-qualified staff members will be responsible for instructing patients/caregivers on the preparation and administration of the correct doses of study medication.

5.5.1.2 Dual chamber pen

Table 3 Identity of investigational product delivered via dual chamber pen

Investigational product	Dosage form and strength	Manufacturer
Exenatide once weekly (EQW)	2.0 mg powder and solvent for prolonged release suspension for injection, prefilled pen ^b	AstraZeneca ^a
Placebo to match exenatide once weekly	Placebo powder and solvent for suspension for injection, prefilled pen ^c	AstraZeneca ^a

^a Responsible for supply of Investigational Product and placebo.

^b Dosage form and strength for non-US sites. For sites in the US only, dosage form and strength are as follows:
Extended release for injectable suspension (2 mg of exenatide per 0.65 mL suspension) in a single dose pen.

^c Dosage form and strength for non-US sites. For sites in the US only, dosage form and strength are as follows:
Placebo powder and solvent for injectable suspension in a single dose pen.

All study medication sufficient for 4-weeks treatment will be packed into patient kits. The prefilled single use injection pens containing the exenatide/placebo will first be individually packed into blister packages and then packed into a box containing 4 prefilled pens.

Study materials will be provided to patients by the Investigator or medically qualified subinvestigator named on Form FDA 1572, or other qualified study-site personnel. Under no circumstance will the Investigator or subinvestigators allow the study medication to be used other than as directed by the protocol or to be administered to any persons other than patients participating in the study. Medically-qualified staff members will be responsible for instructing patients/caregivers on the preparation and administration of the correct doses of study medication.

5.5.2 Formulation, Packaging, and Storage

The EQW is an extended release formulation of exenatide and consists of 5% exenatide, sucrose, and 50:50 poly D,L lactide-co-glycolide.

For use in the prefilled syringes, the EQW microspheres and matching placebo will be supplied in vials containing the white to off white dry powder (40 mg of EQW microspheres).

For use in the dual chamber pen, the exenatide microspheres or matching placebo and the diluent for suspension will be supplied in a prefilled single-use injection pen. Diluent for suspension will be supplied in prefilled syringes. Each syringe will contain 0.75 mL. The EQW or matching placebo dose is prepared by reconstitution of the microspheres in the diluent provided.

For both formulations, the investigational product must be stored in a refrigerator between 2°C and 8°C and protected from light. EQW matching placebo is the identical formulation with the active ingredient omitted. Diluent for suspension of the EQW and placebo microspheres contains carboxymethylcellulose low viscosity, polysorbate 20, sodium chloride, and water for injection.

For both formulations, specific instructions for dose preparation of the EQW injection will be provided in the Patients Instructions for Use. The reconstituted dose of study medication (EQW or matching placebo) should not be stored for future use. The injection must be administered immediately after preparation of the dose.

Packaging

All study medication will be packed into kits with enough for 4-weeks of treatment.

The vials containing the exenatide/placebo powder for injections will be packed into a small box containing 4 vials. Four prefilled syringes with diluent for suspension of EQW and matching placebo will be packed into another box also containing 6 vial adaptors and 6 23-Gauge×5/16 inch needles.

The prefilled single use injection pens containing the exenatide or placebo will first be individually packed into blister packages and then packed into a box containing 4 prefilled pens.

Doses and Treatment Regimens

Doses of study medication are to be injected into SC tissue. The site of injection should be rotated on a regular basis so that the same site is not used repeatedly.

At Visit 2 (Week 0), a medically-qualified staff member will demonstrate the preparation of study medication for the patient. At this visit, the study medication will be administered by a medically-qualified staff member following all study-related procedures.

Caregiver will subsequently administer study medication to the patient (or the patient will self-administer if the medically qualified site staff member assesses that this is appropriate, taking into account the patient's capabilities and characteristics) once weekly (± 2 days), relative to the date of the first dose of exenatide once weekly (Visit 2 [Week 0]), for the duration of the study. On weeks with no scheduled study-site visits, patients may opt to return to the study site to have the injection procedure monitored or provided by study-site personnel, although such visits will not be required. On weeks of scheduled study visits, patients should bring their study medication treatment kit with them to the clinic (if the study visit is scheduled on the same day as patient's weekly administration) and will self-administer study medication after completion of the study procedures (at the study site or after leaving the study site).

Adjustments to dosing regimens are not permitted. If a patient is unable to tolerate the study medication (eg, patient experiences AEs that are judged by the Investigator to be unacceptable), the Sponsor should be contacted to evaluate the patient's continued participation in the study.

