- Approximately 77 patients will be randomly assigned across 2 treatment groups in a 5:2 ratio to receive either subcutaneous (SC) administration of EQW 2 mg or placebo

(PBO), respectively, with at least 50 patients in the exenatide and at least 20 patients in the PBO group.

- Group A: EQW 2 mg (52 weeks)
- Group B: PBO (24 weeks), EQW 2 mg (28 weeks)
- The study includes a 24-week, controlled assessment period, during which patients will receive study medication according to their randomized treatment group, followed by a 28-week, open-label, uncontrolled extension period in which all patients will receive EQW.
- In addition to receiving study medications, all patients will participate in a lifestyle intervention program encompassing diet and physical activity modifications. If patients are taking concomitant antidiabetic medication they should administer their usual concomitant antidiabetic medication therapy at approximately the same time each day throughout the study.
- At Visit 1 (Screening), patients will complete eligibility evaluations and screening procedures. Patients who meet eligibility requirements will be randomly assigned to a treatment group (Group A: EQW 2 mg, Group B: PBO) at Visit 2 (Week 0). At Visit 2 (Week 0), patients will complete baseline safety, efficacy, pharmacodynamic (PD), and pharmacokinetic (PK) assessments. Following baseline assessments, patients and parents/caretaker will be trained on study medication administration and the first dose of study medication will be administered. During the controlled assessment period, patients or parent/caretaker will administer study medication. Patients will return to the study site at 4- or 6-week intervals for safety, efficacy, PD, and PK assessments. On weeks with no scheduled study-site visits, patients may opt to return to the study site to have the injection procedure monitored or provided by study-site personnel.
- Following the 24-week controlled assessment period, all patients will enter the 28-week extension period. During the 28-week extension period, all patients will receive EQW 2 mg for 28 weeks up to Visit 10 (Week 52/End of Treatment). The patients will return to the study site at 6- or 12-week intervals for safety, efficacy, PD, and PK assessments and will complete study termination procedures at Visit 11 (Week 62/Study Termination).

The overall study design is shown [below](#).

Randomization 5:2

Abbreviations: EQW, exenatide once weekly; P, phone call

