- Following the controlled assessment period, all patients enter a 28-week extension period. Group A patients will continue to receive EQW for an additional 28 weeks up to Visit 10 (Week 52). Group B patients will initiate treatment with EQW for 28 weeks up to Visit 10 (Week 52). During the 28-week extension period, patients will be required to return to the clinical study site at 6-, 10-, and 12-week intervals at Visit 8 (Week 28), Visit 9 (Week 40), and Visit 10 (Week 52) for efficacy, safety, PD, and PK assessments.
- At Week 26 of the controlled assessment period, patients will be contacted by phone by qualified study-site personnel to discuss study compliance, address any questions related to study medication, and review AEs
- Patients who withdraw from the investigational product after Visit 2 (Week 0) and prior to Visit 10 (Week 52) will be invited to return to the study site for an Early Termination visit for HbA1c, fasting plasma glucose, body weight, and clinical safety laboratory measures.
- All visits scheduled during the 24-week controlled assessment and 28-week extension period should occur within ± 2 days of the scheduled date relative to Visit 2 (Week 0).
- All patients will return to the site on Visit 11 (Week 62/Study Termination).

A detailed schedule of study procedures by visit is presented in [Table 1](#) (Study Plan).

Table 1
Study Plan

Evaluation	Visit 1 Screening	Controlled Assessment Period 24 weeks										Extension Period 28 Weeks			Visit 11 Week 62* (Study Termination)	Early Termination	
		Visit 2 Week 0	Week 2 Phone Call	Visit 3 Week 4	Visit 4 Week 8	Visit 5 Week 12	Visit 6 Week 16	Week 16 Phone Call	Visit 7 Week 18	Visit 7 Week 24	Week 26 Phone Call	Visit 8 Week 28	Visit 9 Week 40	Visit 10 Week 52 (End of Study Treatment)			
Fast (≥8 Hours Prior to Visit)	X	X	X	X	X	X	X	X	X	X	X	X	X	X	X	X	X
Informed Consent/Patient Assent/HIPAA	X																
Review of Inclusion and Exclusion Criteria	X	X															
Randomization		X															
Complete Medical History/Urine Drug and Alcohol Screen	X																
Adverse Event Assessment		X	X	X	X	X	X	X	X	X	X	X	X	X	X	X	X
Concomitant Medication Review	X	X	X	X	X	X	X	X	X	X	X	X	X	X	X	X	X
Physical Examination		X			X									X			X
ECG		X															
Body Weight, Height, and Vital Signs	X	X	X	X	X	X	X	X	X	X	X	X	X	X	X	X	X
Blood Sample for Serum βHCG Test (Females)	X															X	X

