Return Used/Unused Study Medication			X	X	X	X	X					X	X	X	X

Abbreviations: β hCG, human chorionic gonadotropin, beta subunit; CEA, carcinoembryonic antigen; DHEAS, dehydroepiandrosterone; ECG, electrocardiogram; FSH, follicle-stimulating hormone; HbA1C, hemoglobin A1C; HDL-C, high-density lipoprotein cholesterol; HIPAA, Health Insurance Portability and Accountability Act; LH, luteinizing hormone; GAD65, glutamic acid decarboxylase; ICA512, islet cell antigen; IGF-1, insulin-like growth factor-1; LDL-C, low-density lipoprotein cholesterol; free T4, thyroxine; SHBG, sex hormone-binding globulin; TC, total cholesterol; TG, triglycerides; TSH, thyroid stimulating hormone.

Note: Study plan applies only to the 24-Week Controlled Assessment Period and 28-Week Extension Period of Study BCB114. See [Appendix E](#) for details of study procedures for the Extended Safety Follow-up Period.

*Visit 11 should take place 10 weeks after last dose of EQW and no later than 12 weeks

[1] If the study visit is scheduled on the same day as the patient's weekly administration of study medication, patient and/or caregiver will administer the study medication at the study site after completion of all other study procedures.

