6.2 Data collection at enrollment and follow-up

6.2.1 Enrollment procedures

The procedures to be performed during the study are listed by visit in [Table 1](#) (Study Plan). Specific procedures to be performed during the study by visit are described in detail in Sections [6.2.2](#) and [6.2.3](#).

All patients will be instructed to arrive in the morning of each scheduled study visit. Patients are to have fasted overnight (no food or beverage except water) for ≥ 8 hours at Visit 1

(Screening), Visit 2 (Week 0), Visit 3 (Week 4), Visit 4 (Week 8), Visit 5 (Week 12), Visit 7 (Week 24), and Visit 10 (Week 52/End of Treatment) or Early Termination. If the study visit is scheduled on the same day as the patient's weekly administration of study medication, patients will be instructed to delay administration of study medication, bring their study medication to the study site, and administer study medication at the study site. If patients are taking concomitant antidiabetic medication they should administer their usual concomitant antidiabetic medication therapy at approximately the same time each day throughout the study.

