6.2.3.2 Week 2 – Telephone contact

The Investigator and/or qualified study-site personnel will contact patients by telephone at Week 2 to discuss study compliance, address any questions related to study medication administration, and review AEs.

6.2.3.3 Visit 3 (Week 4) and Visit 4 (Week 8) – (Controlled assessment period)

Prior to Visit 3 (Week 4) and Visit 4 (Week 8), patients will have fasted overnight (≥ 8 hours). If the study visit is scheduled on the same day as the patient's weekly administration of study medication, patients should delay administration of study medication on the morning of the study-site visit and bring the study medication to the site.

All patients will undergo the following procedures:

- Review of concomitant medication and AEs
- Body weight, height, and vital signs will be measured
- Urine will be collected for a pregnancy test (females only)
- Injection site reaction assessment will be performed
- Blood samples will be collected for:
 - HbA1c
 - Fasting plasma glucose
 - Fasting insulin
 - Measurement of plasma exenatide
 - Measurement of antibodies to exenatide.
- Patients will receive diet and nutritional counseling
- Patients will have a study medication compliance review
- Study medication will be dispensed
- Patient and/or parent/caregiver will administer study drug at the study site (if applicable)
- Patients will be asked to return used/unused study medication.

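### Protocol 5.5.2 contradicts itself on who injects in visit weeks: one sentence has patients self-administer unconditionally, against the caregiver-by-default rule in the same paragraph

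*Protocol*

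**What the plan says.** Under Doses and Treatment Regimens, Protocol 5.5.2 has site staff give the Visit 2 dose and then sets the rule for every later dose: "Caregiver will subsequently administer study medication to the patient", with the exception that "the patient will self-administer if the medically qualified site staff member assesses that this is appropriate", taking account of the child's capabilities and characteristics. The rule runs weekly from the first dose to the end of the study.

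The same paragraph closes with a sentence on weeks that contain a scheduled visit. Patients bring their kit if the visit falls on the dosing day, and they "will self-administer study medication after completion of the study procedures (at the study site or after leaving the study site").

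Other current text on the same subject:

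- Synopsis, Study Design and Methods: "During the controlled assessment period, patients or parent/caretaker will administer study medication".
- Table 1, footnote [1], for visits on the dosing day: "patient and/or caregiver will administer the study medication at the study site after completion of all other study procedures".
- Visit procedure lists in 6.2.3.3, 6.2.3.4, 6.2.3.6, 6.2.3.7 and 6.2.3.9: "Patient and/or parent/caregiver will administer study drug at the study site (if applicable").
- 6.2.1, for visits on the dosing day: "patients will be instructed to delay administration of study medication, bring their study medication to the study site, and administer study medication" at the site.
- Appendix F, 9.1.1 (mixed-meal substudy, Visit 2): subjects are told to hold off injecting until the blood draws and main-protocol procedures are finished.

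The version history says the current amendment clarified dosing so that caregivers inject after Visit 2 and patients do so only when staff find it appropriate. The stated aim was to reduce the risk of unsuitable self-administration.

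**The concern.** Eligibility starts at age 10, and the product must be reconstituted and injected at once. Whether a given child can do this safely is the judgement that 5.5.2 gives to qualified site staff. The visit-week sentence drops both the caregiver and that judgement. For a child assessed as unsuitable, the two sentences cannot both be followed on a visit dosing day.

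The protocol also says that study medication may be used only as it directs (5.5.1.1 and 5.5.1.2) and that the investigator is not to deviate from it (8.5). A site that does the sensible thing and lets the caregiver inject departs from the closing sentence. A site that follows the closing sentence departs from the safeguard. What is at stake is clear dosing conduct and safety in those children.

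**Working it through.** The plan gives no figure to reproduce, so the check is a comparison of text followed by a count of visits.

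**1. Does the rule cover visit weeks?** Yes. The opening sentence applies for the whole study and makes no exception for weeks with a visit, so both sentences govern the same doses.

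**2. Do the two sentences agree on those doses?**

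| Element | 5.5.2, opening sentence | 5.5.2, visit-week sentence |
|---|---|---|
| Default injector | Caregiver | Patient |
| Patient may inject | If staff assess it as appropriate | Always |
| Caregiver named | Yes | No |

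They agree only for patients already assessed as suitable.

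**3. Could self-administer be shorthand for patient or caregiver?** Not within this paragraph. The opening sentence uses the term in contrast to the caregiver giving the dose. The visit-week sentence is also the more specific of the two, so a reader could take it as the rule for those weeks.

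**4. Do other lines share the fault?**

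- The synopsis, Table 1 footnote [1] and the five visit lists name both patient and caregiver. They do not repeat the staff assessment, but they do not exclude it, and the 5.5.2 rule supplies it.
- 6.2.1 names only patients, but its verb is administer. The visit sections have a similar pattern: patients are told to delay the dose, and the list below then names patient or caregiver. 6.2.1 leaves out a role and does not contradict the rule.
- Appendix F, 9.1.1 reads as if subjects inject at Visit 2, whereas 5.5.2 and 6.2.3.1 have staff give that dose. Appendix F, section 8 also names only subjects, but it refers back to the main protocol.

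**5. How many occasions?** Scheduled visits after Visit 2 with dosing in their procedure list are Visits 3 to 9, at Weeks 4, 8, 12, 18, 24, 28 and 40: 9 − 3 + 1 = 7. Section 3.1 also speaks of a last dose at Visit 10 (Week 52). If that dose is given, the count is 7 + 1 = 8, although 6.2.3.10 lists no dosing.

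Weekly doses are timed from Visit 2 with a window of 2 days either way. Visits have the same window "of the scheduled date relative to Visit 2 (Week 0"). A visit on the dosing day is therefore the planned case, though not a certain one. Seven is an upper limit on occasions per patient and does not measure harm.

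**The case against.** The best reply is that sites are already pointed to the right conduct. The 5.5.2 rule comes first, the version history states its purpose, and Table 1 and the lists for Visits 3 to 9 name the caregiver for the same doses. The ambiguity also arises around a site visit, where the staff who judge suitability are at hand. Most of this stands, and it is why the point is minor. It does not remove the contradiction: the clause is unconditional, sits in the paragraph that sets the rule, and also covers doses given after the patient has left the site.

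A reader might infer that 6.2.1 likewise tells unsuitable children to self-inject. The documents do not support that, because 6.2.1 does not say self-administer and the 5.5.2 rule, footnote [1] and the visit lists fill the gap.

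A reader might also see a hazard in the place of dosing, since 5.5.2 allows it after leaving the site while 6.2.1 and footnote [1] put it at the site. Both 5.5.2 and footnote [1] place the dose after the visit procedures, and 6.2.1 says to delay it, so no harm follows from the difference.

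**Conclusion.** The contradiction within 5.5.2 is real and lies wholly in current operative text. The version history shows what was intended, but the conclusion does not depend on it. The consequence is confined to children assessed as unsuitable for self-injection, on at most seven visits each (eight if a Week 52 dose is given). The documents do not give the number of such children, so no share of patients or doses is claimed.

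It would go too far to conclude that the protocol as a whole directs self-injection at visits, since its other dosing lines permit the caregiver. It would also go too far to expect any effect on the primary analysis, which does not depend on who gives the injection. The design rule itself is sound. This is a minor drafting inconsistency in safety wording.

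**What to change.** In the visit-week sentence of 5.5.2, replace the self-administration clause with wording such as: *and the caregiver (or the patient, where qualified site staff have assessed self-administration as appropriate) will administer the dose*, keeping it after the visit procedures.

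Tidy-ups, not corrections of error:

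- In 6.2.1, name the caregiver, with the same condition for the patient, in the dosing-day sentence.
- In Appendix F, 9.1.1, say that the Visit 2 dose is given by site staff once the blood draws and other procedures are complete.
- Optionally, choose one wording for place of dosing and use it in 5.5.2, 6.2.1 and Table 1 footnote [1]. The visit lists fit either choice.

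The necessary change is one sentence. It adds no visit, procedure or staff. It can be bundled with the next amendment, which needs IRB approval before implementation (8.5), and it helps only patients still being dosed at that point.
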